### Schema

Cycle = 28 days  
Accrual Goal: 70

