The Comprehensive Adverse Events and Potential Risks list (CAEPR) provides a single list of reported and/or potential adverse events (AE) associated with an agent using a uniform presentation of events by body system. In addition to the comprehensive list, a subset, the Specific Protocol Exceptions to Expedited Reporting (SPEER), appears in a separate column and is identified with bold and italicized text. This subset of AEs (SPEER) is a list of events that are protocol specific exceptions to expedited reporting to NCI (except as noted below). Refer to the 'CTEP, NCI Guidelines: Adverse Event Reporting Requirements' [http://ctep.cancer.gov/protocolDevelopment/electronic\\_applications/docs/aeGUIDELINES.pdf](http://ctep.cancer.gov/protocolDevelopment/electronic_applications/docs/aeGUIDELINES.pdf) for further clarification. *Frequency is provided based on 2069 patients.* Below is the CAEPR for BMS-936558 (Nivolumab, MDX-1106).

**NOTE:** If an AE meets the reporting requirements of the protocol, and it is listed on the SPEER, it should **ONLY** be reported via CTEP-AERS if **the grade being reported exceeds the grade listed in the parentheses next to the event in the SPEER.**

Version 2.3, June 18, 2018

Adverse Events with Possible Relationship to BMS-936558 (Nivolumab, MDX-1106) (CTCAE 5.0 Term) [n= 2069]			Specific Protocol Exceptions to Expedited Reporting (SPEER)
Likely (>20%)	Less Likely (<=20%)	Rare but Serious (<3%)	
BLOOD AND LYMPHATIC SYSTEM DISORDERS			
	Anemia		Anemia (Gr 2)
CARDIAC DISORDERS			
		Cardiac disorders - Other (cardiomyopathy)	
		Myocarditis	
		Pericardial tamponade 	
		Pericarditis	
ENDOCRINE DISORDERS			
	Adrenal insufficiency 		
	Hypophysitis 		
	Hyperthyroidism 		
	Hypothyroidism 		
EYE DISORDERS			
		Blurred vision	
		Dry eye	
		Eye disorders - Other (diplopia) 	
		Eye disorders - Other (Graves ophthalmopathy) 	
		Eye disorders - Other (optic neuritis retrobulbar) 	
	Uveitis		
GASTROINTESTINAL DISORDERS			
	Abdominal pain		Abdominal pain (Gr 2)
	Colitis 		

Adverse Events with Possible Relationship to BMS-936558 (Nivolumab, MDX-1106) (CTCAE 5.0 Term) [n= 2069]			Specific Protocol Exceptions to Expedited Reporting (SPEER)
Likely (>20%)	Less Likely (<=20%)	Rare but Serious (<3%)	
		Colonic perforation 	
	Diarrhea		Diarrhea (Gr 3)

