Grade 4	Off treatment
Patients with fever should be evaluated as clinically appropriate. Patients may experience isolated fever during infusion reactions or up to several days after infusion. Evaluation over the course of 1-2 weeks should be done for other autoimmune events that may present as fever	

Fever	Management/Next Dose for Nivolumab combination
≤ Grade 1	Evaluate and continue at same dose level
Grade 2	Hold until ≤ Grade 1. Resume at same dose level.
Grade 3	Hold until ≤ Grade 1. Resume at same dose level.
Grade 4	Off treatment
Patients with fever should be evaluated as clinically appropriate. Patients may experience isolated fever during infusion reactions or up to several days after infusion. Evaluation over the course of 1-2 weeks should be done for other autoimmune events that may present as fever	
See Section 5 . Infusion reactions	

Rev. 3/17

Cardiac*	Management/Next Dose for BMS-936558 (Nivolumab) Cardiac Toxicities
≤ Grade 1	Hold dose pending evaluation and observation.** Evaluate for signs and symptoms of CHF, ischemia, arrhythmia or myositis. Obtain history EKG, CK (for concomitant myositis), CK-MB. Repeat troponin, CK and EKG 2-3 days. If troponin and labs normalize may resume therapy. If labs worsen or symptoms develop then treat as below. Hold pending evaluation
Grade ≥ 2 with suspected myocarditis	Hold dose.** Admit to hospital. Cardiology consult. Rule out MI and other causes of cardiac disease. Cardiac Monitoring. Cardiac Echo. Consider cardiac MRI and cardiac biopsy. Initiate high dose methylprednisolone. If no improvement within 24 hours, add either infliximab, ATG or tacrolimus. Resume therapy if there is a return to baseline and myocarditis is excluded or considered unlikely.
Grade ≥ 2 with confirmed myocarditis	Off protocol therapy. Admit to CCU (consider transfer to nearest Cardiac Transplant Unit). Treat as above. Consider high dose methylprednisolone. Add ATG or tacrolimus if no improvement. Off treatment.

* Including CHF, LV systolic dysfunction, Myocarditis, CPK, and troponin
 
** Patients with evidence of myositis without myocarditis may be treated according as "other event"
 
Note: The optimal treatment regimen for immune mediated myocarditis has not been established. Since this toxicity has caused patient deaths, an aggressive approach is recommended.
	

- Drug will be held for grade 2 cardiac dysfunction pending evaluation

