- Drug will be permanently discontinued for grade 3 or 4 cardiac dysfunction and grade 2 events that do not recover to baseline or that reoccur
- Treatment with steroids as clinically indicated

If treatment is delayed >6 weeks for an adverse event, the study PI must be consulted for any consideration of further therapy.

Patients with grade 3 thyroiditis and skin rash may continue therapy as for grade 2 events with resolution and stable replacement treatment.

Patients with thyroiditis or hypopituitarism who are stable as above may be restarted with replacement hormones including thyroid hormone and physiologic doses of corticosteroids.

Please note that grading and for hypophysitis with symptoms of headache, visual or neurologic changes or radiologic evidence of pituitary enlargement and other CNS events such as aseptic meningitis or encephalitis should be considered grade 3 events.

Any patients who require additional immune suppressive treatment beyond steroids should go off study treatment

Patients requiring > two dose delays for the same event should go off protocol therapy.

Prior to starting corticosteroids or hormone replacement for any reason, appropriate endocrine testing including cortisol, ACTH, TSH and T4 should be obtained to document baseline. However, if urgent steroid use is clinically required, steroid treatment should not be delayed for bloodwork.

Please note that in some cases the treatment algorithms recommend steroids if symptoms do not resolve in 7 days. However, this recommendation is not meant to delay steroid treatment at any time it is clinically indicated.

Patients may be dose-delayed for evaluation and restarted depending on results.

Any patient started on corticosteroids initially who is determined to not require steroid treatment for an autoimmune adverse event may resume therapy after a 2 week observation period without further symptoms at the discretion of the PI or investigator.

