## GI Adverse Event Management Algorithm

[figure not shown]
Rule out non-inflammatory causes. If non-inflammatory cause is identified, treat accordingly and continue I-O therapy. Opiates/narcotics may mask symptoms of perforation. Infliximab should not be used in cases of perforation or sepsis.

Patients on IV steroids may be switched to an equivalent dose of oral corticosteroids (e.g. prednisone) at start of tapering or earlier, once sustained clinical improvement is observed. Lower bioavailability of oral corticosteroids should be taken into account when switching to the equivalent dose of oral corticosteroids.

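### The cardiac table in Section 3.4 gives confirmed grade 2 or higher myocarditis weaker steroid wording than suspected disease, and leaves infliximab's status unclear

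*Protocol*

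**What the plan says.** The cardiac table in Protocol Section 3.4 has separate rows for suspected and confirmed myocarditis of grade 2 or higher.

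- **Suspected.** Hold nivolumab, admit, obtain a cardiology consult, monitor and obtain an echocardiogram. MRI and biopsy are to be considered. Then: "Initiate high dose methylprednisolone. If no improvement within 24 hours, add either infliximab, ATG or tacrolimus".
- **Confirmed.** Stop protocol therapy and admit to a coronary care unit, with possible transfer to a transplant centre. Then: "Treat as above. Consider high dose methylprednisolone. Add ATG or tacrolimus if no improvement".
- **Note under the table.** It says that no optimal regimen has been established, and then: "Since this toxicity has caused patient deaths, an aggressive approach is recommended".
- **Text after the table.** One bullet reads "Treatment with steroids as clinically indicated". A later paragraph on endocrine testing adds that "if urgent steroid use is clinically required, steroid treatment should not be delayed for bloodwork".

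**The concern.** The confirmed row contradicts itself on the steroid. Its opening back-reference carries over a direct order to start high-dose methylprednisolone, and the next sentence turns that order into something to consider. A site working from this row alone could read the steroid as optional in the condition that the table itself says has killed patients.

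The row also restates the second-line agents and leaves out infliximab, which the back-reference would allow. A site facing a confirmed case that is not improving cannot tell whether infliximab may be used. Patient safety is at stake here; no trial statistic is.

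**Working it through.** No plan figure needs to be reproduced, so the check compares the two rows, looks for text elsewhere that settles the difference, and then bounds the number of patients.

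**1. The two rows side by side**

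| Item | Suspected row | Confirmed row, via the back-reference | Confirmed row, own wording | Result |
|---|---|---|---|---|
| Steroid | Initiate | Initiate | Consider | 1 conflict |
| Second-line agents | Infliximab, ATG, tacrolimus (3) | The same 3 | ATG, tacrolimus (2) | 1 agent unclear |
| Time to escalation | 24 hours | 24 hours | None stated | No conflict |

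**2. Are the two verbs interchangeable?** No. The suspected row uses *consider* for optional steps (MRI and biopsy) and, immediately afterwards, *initiate* for the steroid. Within one cell the table already separates an option from an action.

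**3. Is the second-line difference a contradiction?** Not strictly. The two-agent list is a subset of the three-agent list (overlap 2, 3 − 2 = 1 left over), so adding ATG or tacrolimus satisfies both rows. Only infliximab is open. Where the protocol means to bar that drug it says so: the GI algorithm in Appendix II states "Infliximab should not be used in cases of perforation or sepsis". No comparable sentence covers confirmed myocarditis.

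**4. Does other text settle it?**

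- The bullet on steroids after the table is general and does not choose between the verbs.
- The sentence on urgent steroids concerns delay for blood tests, not whether steroids are given.
- The title of Appendix II lists endocrine, gastrointestinal, hepatic, neurological, pulmonary, renal and skin algorithms. No cardiac algorithm is named, so the figures not shown are unlikely to help.
- Section 3.4 also points to the Investigator Brochure, which was not available for this review.

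**5. How many patients?** The adverse event list in Section 3.3 places myocarditis in its rare-but-serious column, headed as below 3%. The Schema gives "Accrual Goal: 70".

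- At the accrual goal: fewer than 0.03 × 70 = 2.1 expected cases of any grade.
- For the cohort of 47 mentioned in Appendix V, Section IV.C: fewer than 0.03 × 47 = 1.41.

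These bound the expected count and do not cap the number of cases. They rest on a column heading, not on a rate for this trial. Confirmed cases of grade 2 or higher are a part of this count; the protocol does not give their rate.

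**The case against.** The strongest reply is that the confirmed row already orders the steroid, because the back-reference comes first. A confirmed case will normally have been a suspected one, so methylprednisolone should already be running. In other respects the confirmed row is the more aggressive of the two: coronary care, possible transfer to a transplant centre, and a permanent stop in place of a hold. The note concedes that no optimal regimen is established, which gives some reason for discretionary wording. Section 3.4 describes its tables as guidelines and recommends consulting the study chair. On infliximab, nothing in the text prohibits it.

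Much of this stands, and it limits the practical risk. It does not remove the conflict. The lack of an established regimen might justify discretion in both rows, but it does not explain why the discretion appears only in the graver one. Guideline status does not make the wording harmless either, because sites are expected to act on these tables. Being off protocol therapy settles nivolumab dosing, but the row still directs acute treatment and should be safe to read alone. The infliximab part does reduce to a query, since the sponsor's intent cannot be inferred from the protocol.

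**Conclusion.** The point holds on the steroid. The confirmed-myocarditis row is wrong as written: it orders high-dose methylprednisolone by reference and then downgrades it to an option, against the table's own call for aggressive treatment. Infliximab's status is unclear, but that is a question for the sponsor and not an established error. The missing 24-hour limit is not a contradiction, because the back-reference supplies it.

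The size is one table row, with one wording conflict and one open question. Fewer than 2.1 myocarditis cases of any grade would be expected among 70 patients, assuming that the column heading of below 3% applies to this population. The remaining risk is a site that works directly from the confirmed row. The rule to stop nivolumab, the endpoints and the analysis are untouched. The row should be corrected because the event can be fatal and the correction is simple.

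**What to change.** In the confirmed row, replace the steroid and second-line sentences with a direct instruction: start, or continue, high-dose methylprednisolone; if there is no improvement within 24 hours, add an agent from one explicit list.

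The study chair and the drug sponsor should decide whether infliximab is on that list. If it is deliberately excluded in confirmed disease, the row should say so, as the GI algorithm does for perforation or sepsis, and the back-reference should be limited to work-up and monitoring.

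The cost is a wording change to one row at the next amendment. It adds no procedures, visits or data.

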3.4 Dose Modifications

All toxicity grades below are described using the NCI Common Terminology Criteria for Adverse Events (CTCAE) version 4.0.

All appropriate treatment areas should have access to a copy of the CTCAE version 4.0. A copy of the CTCAE version 4.0 can be downloaded from the CTEP website (<http://ctep.cancer.gov>).

*Please refer to the Nivolumab Investigator Brochure or [Appendix II](#) to the protocol for toxicity management algorithms which include specific treatment guidelines. These algorithms should be followed unless there are specific clinical circumstances for which the treating physician decides an alternative treatment approach is clinically appropriate. Consultation with the study chair is recommended.*

*In all of the tables for dose modification and holds in this section, the guidelines are for adverse events thought at least possibly attributed to study drug. Generally we strongly encourage early evaluation while withholding drug, and appropriate treatment as indicated in the management tables and event specific guidelines.*

Rev. 3/17

ALL OTHER EVENTS	Management/Next Dose for Nivolumab
≤ Grade 1	No change in dose
Grade 2	Hold until ≤ Grade 1 OR baseline (exceptions as noted below)
Grade 3	Off protocol therapy (exceptions as noted below)
Grade 4	Off protocol therapy
Recommended management: As clinically indicated	

- Any grade 2 drug-related uveitis or eye pain or blurred vision that does not respond to topical therapy and does not improve to Grade 1 severity within the re-treatment period OR requires systemic treatment should go off protocol treatment
- Any adverse event, laboratory abnormality, or intercurrent illness which, in the judgment of the investigator, presents a substantial clinical risk to the subject with continued study drug dosing should go off protocol treatment.
- Any grade 2-4 drug-related laboratory abnormality or electrolyte abnormality, that can be managed independently from underlying organ pathology with electrolyte replacement, hormone replacement, transfusion or insulin or that does not require treatment does not require hold/discontinuation.
- Tolerable and clinically stable grade 2 toxicities attributed to study drug may remain on study with PI approval (e.g. thrombosis that is being anticoagulated)

Rev. 12/16

Rev. 3/17

Rev. 3/17

Skin Rash and Oral Lesions	Management/Next Dose for Nivolumab
≤ Grade 1	No change in dose *

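### Section 3.4 says both resume and permanently stop after some recovered grade 3-4 cardiac dysfunction; the Section 3.7 size cap, read literally, shuts out every patient progressing from baseline

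*Protocol*

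**What the plan says.** **Cardiac rule (Protocol, Section 3.4).** The cardiac table has a row headed "Grade ≥ 2 with suspected myocarditis". It holds drug, calls for admission, work-up and high-dose steroid, and closes with "Resume therapy if there is a return to baseline and myocarditis is excluded or considered unlikely". The table's footnote gives its scope: "Including CHF, LV systolic dysfunction, Myocarditis, CPK, and troponin". Of the bullets under the table, one holds drug for grade 2 dysfunction while it is evaluated. The next reads "Drug will be permanently discontinued for grade 3 or 4 cardiac dysfunction" and adds "grade 2 events that do not recover to baseline or that reoccur". The opening of Section 3.4 says of its tables that "the guidelines are for adverse events thought at least possibly attributed to study drug". Later in the section: "Any patients who require additional immune suppressive treatment beyond steroids should go off study treatment".

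**Continuation rule (Protocol, Section 3.7).** Patients with a first RECIST 1.1 progression within 24 weeks may stay on drug if they meet a list of conditions. One unpunctuated bullet allows at most four new lesions and also says that the total sum of diameters, new lesions included, may not exceed 40% of the initial sum. The word increase does not appear.

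**The concern.** Both passages decide who goes on receiving nivolumab, and sites have to apply them at the bedside.

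In the cardiac case, two sites reading the same page could treat the same recovered patient in opposite ways: one re-exposes, the other stops for good. A judgement that myocarditis is unlikely still leaves some chance that it was present, and the Protocol notes that this toxicity has caused deaths.

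In the progression case, the condition is set at a level that patients growing from baseline cannot reach. The section exists to let selected patients continue past an initial progression. A site that follows the text must refuse most of them, while a site that guesses the intent will not. These are two independent errors with the same kind of consequence.

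**Working it through.** **1. Cardiac: the two rules side by side (Section 3.4)**

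- *Grade.* The row starts at grade 2 with no ceiling, so it includes grades 3 and 4. The bullet names grades 3 and 4.
- *Event.* The footnote puts heart failure and left ventricular systolic dysfunction in the table. Both are cardiac dysfunction in the bullet's sense, so the rules overlap there.
- *Recovery.* The row makes recovery a route back to drug. In the bullet, the recovery and recurrence clause attaches to grade 2 events ("grade 2 events that do not recover to baseline or that reoccur"). The preceding bullet, which holds drug at grade 2, fits that reading: hold grade 2, stop grade 3-4, stop grade 2 if it fails to recover or comes back.
- *Attribution.* The tables cover events at least possibly due to drug. Excluding myocarditis does not always remove that attribution: the adverse event list in Section 3.3 carries cardiomyopathy as a possibly related event, separate from myocarditis.
- *Treatment given.* The row adds infliximab, ATG or tacrolimus if there is no improvement within 24 hours. Those patients leave treatment under "Any patients who require additional immune suppressive treatment beyond steroids should go off study treatment", so only patients managed with no more than steroids remain in conflict.

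The conflict therefore covers patients who meet all of these conditions: grade 3-4 dysfunction; possibly drug-related; recovered to baseline; no immune suppression beyond steroids; myocarditis suspected, then excluded or thought unlikely. The row says resume and the bullet says stop permanently. The number of such patients cannot be derived, because the Section 3.3 list does not count suspected-then-excluded cases.

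**2. The Section 3.7 cap**

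Inputs: cap 40% of the initial sum (Section 3.7); 28-day cycles (Schema); disease measured every 2 cycles (Section 4.1, footnote D). Assumptions: progression in target lesions means growth of at least 20% over the smallest earlier sum (the Protocol cites RECIST 1.1 without stating the threshold); scans on schedule; total sum = target lesions plus measurable new lesions.

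- Ratio for growth g from baseline: total / initial = 1 + g. For g from 0% to 40% this is 1.00 to 1.40, always above 0.40. The result does not depend on the 20% assumption.
- Initial sum 100 mm: cap = 0.40 × 100 = 40 mm; progression from baseline = 1.20 × 100 = 120 mm; 120 / 40 = 3.0, the same at any baseline size.
- Scan interval: 2 × 28 = 56 days = 8 weeks, so weeks 8, 16 and 24. At week 8 the only earlier scheduled measurement is baseline, so progression by target growth cannot meet the cap.
- At weeks 16 and 24: 1.20 × nadir ≤ 40 mm gives nadir ≤ 33.3 mm, a prior shrinkage of at least 66.7%.
- Progression by new or non-target lesions: the total must be ≤ 40 mm. If no new lesion is measurable, target lesions must have shrunk by at least 60%; one measurable 10 mm new lesion lowers the room to 30 mm, or 70%.

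Three readings of the bullet, initial sum 100 mm, no new lesions:

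| Target sum | Level (literal), limit 40 mm | Increase of at most 40%, limit 140 mm | New lesions only, limit 40 mm |
|---|---|---|---|
| 125 mm | stop | may continue | may continue |
| 150 mm | stop | stop | may continue |

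The readings give different decisions for the same scan.

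**The case against.** **Cardiac.** The strongest reply is that Section 3.4 already handles this patient. General sentences there let patients restart after evaluation, and let a patient put on steroids who proves not to need them for an autoimmune event resume after a two-week observation period. Investigators may stop drug for substantial clinical risk, study chair consultation is recommended, and the study PI must be consulted after a delay of more than 6 weeks. All of that is true. But the restart sentences carry no grade limit and no precedence over the bullet. They add weight to the resume side without settling the question, and the safeguards do not say which rule governs.

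A reader might infer that row and bullet cover the same events throughout. The documents do not support that: the footnote also takes in CPK and troponin, and an isolated laboratory rise need not be cardiac dysfunction. Nor does the text allow restart after confirmed myocarditis, which has its own row taking the patient off therapy. Events that do not recover are also outside the conflict.

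One could stretch the bullet's recovery clause over grades 3 and 4. That would remove the conflict, but it strains the sentence and ignores the grade 2 bullet before it.

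**Cap.** The bullet runs two statements together, and punctuation may have been lost when the PDF was read. If the 40% applied to the new lesions' own sum, four 10 mm lesions (40 mm against an initial 100 mm) would just satisfy it. That reading fits poorly with wording that speaks of a total sum with new lesions included. Restoring a break between the two statements gives exactly the literal level, so lost punctuation would not explain the problem away. What stands is that the bullet is open to more than one repair.

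A reader might also infer that no patient at all could qualify. That goes too far: deep prior shrinkage makes the cap reachable. Nor is the efficacy analysis distorted, since Section 3.7 dates progression from the first assessment that exceeds standard criteria.

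**Conclusion.** Both rules are wrong as written and should be fixed.

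The cardiac conflict is real but narrow, confined to the recovered grade 3-4 dysfunction defined above. Few patients will meet those conditions, and no count can be given from the documents. Its weight comes from the consequence, re-exposure after a severe cardiac event, rather than from frequency. It rests on reading the recovery clause with grade 2, as the grammar and the preceding bullet indicate.

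The Section 3.7 cap, read literally, is unworkable for its main purpose: a patient progressing from baseline is at 1.00 or more against a limit of 0.40, and at three times the limit if progression means 20% growth. An increase of at most 40% is the likely intent, but the text does not say so, and the sponsor has to confirm it. The effect is on who may continue treatment; the progression date and the response endpoint are untouched.

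**What to change.** **Section 3.4.** Add an exception to the resumption sentence in the suspected-myocarditis row, for example: *except grade 3-4 cardiac dysfunction, for which drug is permanently discontinued (see bullet below), notwithstanding the general restart provisions*. This is better than limiting the whole row to grade 2, which would also change the handling of isolated CPK and troponin rises. If the sponsor does intend resumption at grade 3-4 once myocarditis is excluded, write that exception into the bullet instead.

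**Section 3.7.** Split the bullet into two conditions: *at most 4 new lesions*; and *the total sum of diameters, including measurable new lesions, may not exceed the baseline sum by more than 40%*. The sponsor should first confirm that an increase over baseline is meant.

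The cost is a short wording change in each section at the next amendment, with no added visits, scans or patients.
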